3.2 Sample Size

We will recruit 400 PSH resident participants, with 200 each in the intervention and wait-list control arms (~20 participants per site). We expect to enroll 100 PSH staff, approximately 5 staff per site.

3.3 Primary Completion

The expected primary completion date is 14 months after the study opens to accrual.

3.4 Study Completion

The expected study completion date is 2 years after the study opens to accrual.

4 Selection and Enrollment of Participants

4.1 Eligibility Criteria

4.1.1 Inclusion Criteria

In order to be eligible to participate in this study, an individual must meet all of the following criteria:

1. Age 18 years or older
2. Ability to understand study procedures and to comply with them for the entire length of the study.
3. Ability of individual or legal guardian/representative to understand a written informed consent document, and the willingness to sign it.
4. Current smokers [(smoked at least 100 cigarettes in lifetime, daily or non-daily smoking in the past 7 days and at least 5 cigarettes per day, verified by expired Carbon Monoxide (CO) \geq 8 parts per million (ppm)]⁷⁷ who smoke in their homes.
5. Expect to live in the PSH site for at least 12 months, and
6. English proficient.

4.1.2 Exclusion Criteria

An individual who meets any of the following criteria will be excluded from participation in this study:

1. Contraindication to any study-related procedure or assessment.

4.2 Recruitment Methods

Recruitment schedule. We will recruit 400 PSH resident participants, with 200 each in the intervention and wait-list control arms (~20 participants per site; Figure 6, Table in Recruitment and retainment section in human subjects). Within each site, all resident participants will be informed about the study and invited to participate. We will recruit participants within blocks of four housing sites per month, with each block containing two intervention and two wait-list control sites, and anticipating roll-out of one such block per month. We anticipate completing recruitment and enrollment of all participants in 6 months, allowing for a one-to-two-month extension to complete these activities. We will offer the intervention to the wait-list control participants once all participants in the intervention sites from the same block have completed their 6-month follow-up. We expect to enroll 100 PSH staff. We will obtain information on the total number of residents and staff at each site to provide an estimate of the proportion enrolled in the intervention.

Within each site, study staff will advertise the study to residents the week prior to enrollment by placing flyers at the study site and making announcements at community meetings. After the informational meeting, study staff will be present at the recruitment sites during designated times to screen interested participants for eligibility and enroll those eligible into the study. Study staff will describe the purpose of the study, the study procedures, including risks and benefits, and obtain written informed consent using the teach-to-goal method at the time of eligibility.⁷⁸ Participants will complete the baseline questionnaire and will receive the study staff-delivered intervention within one week of enrollment. We have adjusted the timeline for recruitment, intervention delivery and follow-up to account for extra time that we may need to complete study procedures to follow protocols around social distancing that PSH sites may have put in place due to COVID-19.

Data collection reimbursements. We will reimburse all resident participants with [REDACTED] gift cards for completing the baseline questionnaire, [REDACTED] the 3-month questionnaire and [REDACTED] the 6-

month questionnaire. We will reimburse participants [REDACTED] for each monthly tracking visit in between follow-ups. Participants selected for random air nicotine monitoring at 6 months will be reimbursed [REDACTED] for placing monitors in their home for 7 days. We will reimburse PSH staff with [REDACTED] gift cards for completing the baseline questionnaire, [REDACTED] the 3-month and [REDACTED] the 6-month questionnaires.

Table: Recruitment and intervention roll-out and follow-up schema ^a	Project Year 1												Project Year 2								
	1	2	3	4	5	6	7	8	9	10	11	12	1	2	3	4	5	6	7	8	9
Recruitment of intervention and wait-list control resident participants																					
Intervention group receives SFH intervention																					
Intervention and wait-list group 3-mo follow-up																					
Intervention and wait-list group 6-mo follow-up																					
Air nicotine monitoring at 6-mo follow-up for a random sample of intervention and wait-list group																					
Staff training in intervention properties and 3- and 6-months follow-up																					
Wait-list group receives SFH intervention after intervention group completes 6-mo follow-up																					
Wait-list control 9-month follow-up																					
Wait-list control 12-month follow-up																					
Staff training in wait-list control properties and 3- and 6-months follow-up																					

^a The first 7 months of the project, which will be spent setting up the project, is not represented in the schema (please see timetable).

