3.1 Characteristics

Overview of the intervention. The intervention, delivered by study staff includes: 1) one-on-one counseling to PSH residents who are smokers on how to adopt a smoke-free home, and 2) training for PSH staff on how to provide referrals to cessation services.

Trial design. We have chosen a cluster-randomized, wait-list controlled trial,^{75,76} where PSH sites will be randomized into intervention and wait-list control groups. Those in the wait-list control group will receive usual care first and then cross over to the intervention arm.

Setting. Study procedures will take place in a private room at each PSH site.

Study procedures for PSH resident participants. Eligible resident participants include current smokers [(smoked at least 100 cigarettes in lifetime (i.e. the standard definition for a life-time smoker), daily or non-daily smoking in the past 7 days and at least 5 cigarettes per day, verified by expired Carbon Monoxide (CO) ≥ 8 parts per million (ppm)]⁷⁷ who smoke in their homes and

expect to live in the PSH site for at least 12 months, are ≥ 18 years of age, are English proficient, and are able to provide informed consent. Study staff will advertise the study to residents the week prior to enrollment by placing flyers at the site and making announcements at community meetings. Study staff will be present at the recruitment sites during designated times to screen interested participants for eligibility, obtain written informed consent using the teach-to-goal method,⁷⁸ and enroll those eligible. **The expired CO assessment for eligibility assessment is to ensure that participants recruited are regular smokers who smoke an average of 5 cigarettes per day. To obtain a CO assessment, the participant blows into a handheld CO monitor that records the expired CO reading (Bedfont EC50 Smokerlyser; Bedfont Scientific Ltd). We considered including monolingual Spanish speaking participants in our study, however, the proportion of monolingual Spanish speaking participants is ~ 5% based on estimates from our partner organizations where the study will be conducted. Therefore, we chose to include English speaking participants in this study.**

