Study procedures for PSH staff participants. Eligible PSH staff participants include service staff (e.g., case managers), who are ≥ 18 years of age, are willing to engage in a 2-hour training, and are able to provide informed consent. Staff in each site will be contacted via email, and invited to participate in a 2-hour training. Study staff will screen PSH staff for eligibility, obtain written informed consent using the teach-to-goal method,⁷⁸ and offer dates for the training.

Randomization and allocation. We will randomize 20 PSH sites into intervention and waitlist control arms. We will use the method of restricted randomization—commonly applied in cluster-randomized trials with small numbers of clusters—to ensure an acceptable level of balance across groups at baseline.⁷⁶ First, we will create two sets of 10 housing sites balanced on preexisting variables describing relevant characteristics of sites and their residents, e.g., property size, current smoking-related policies, and geographic location. Second, we will randomly assign one set of sites to intervention and the other to the wait-list control.

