6.2 Study Procedures and Assessments

6.2.1 Screening Period / Visit -1 (Months 1 to 6)

After an individual provides informed consent, the following activities will be performed during the Screening Period:

- Inclusion/exclusion criteria review
- Adverse Events assessment
- Protocol-specific assessments/procedures
- Randomization/Assignment to Intervention
- Administration of study intervention

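### At least 16 of the 20 sites are recruited after one draw has fixed their arm, with no concealment described, so the arms can differ in who enrols

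*Combined protocol and SAP*

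**What the plan says.** **Allocation.** Section 3.1: "We will randomize 20 PSH sites into intervention and waitlist control arms". Two sets of 10 sites are built to balance on features such as property size, smoking policies and location. Then: "Second, we will randomly assign one set of sites to intervention and the other to the wait-list control". Section 9.1.3 repeats the balanced sets.

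**Recruitment.** Section 4.2: "We will recruit participants within blocks of four housing sites per month, with each block containing two intervention and two wait-list control sites", at one block per month. In the same section, "study staff will advertise the study to residents the week prior to enrollment by placing flyers at the study site", and afterwards "study staff will be present at the recruitment sites during designated times to screen interested participants for eligibility and enroll those eligible". Study staff also explain the study and take consent. Participants "will receive the study staff-delivered intervention within one week of enrollment", which can apply at that point only to intervention sites, because wait-list residents are offered counselling after their block's 6-month follow-up. Section 5.1 gives the counselling to study staff as well.

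**Blinding and concealment.** Section 4.7 gives blinding as not applicable. No section says who makes the draw, who is told its result, or whether recruitment material is the same in both arms.

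**Timing of randomisation.** Section 6.2.1 lists "Randomization/Assignment to Intervention" among the screening activities that follow individual consent, and the schedule in section 6.1 marks it in the screening column.

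**The concern.** In a cluster trial, randomising sites balances the sites. It does not balance the volunteers if people decide to join after the arm is fixed and can be known. Here the two arms amount to different offers. An intervention resident gets counselling within a week and finishes in 6 months. A wait-list resident waits until the block's 6-month follow-up is complete and stays for a year, with extra visits at 9 and 12 months.

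The primary outcome is self-reported voluntary adoption of a smoke-free home, which is likely to depend on motivation. If motivated residents volunteer at different rates by arm, the 6-month comparison mixes the intervention effect with a difference in who was enrolled. Later analysis cannot fully separate the two.

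**Working it through.** **1. How many sites are recruited after allocation?**
- Blocks: 20 sites / 4 per block = 5 monthly blocks (sections 3.1, 4.2).
- One draw assigns a whole set of 10, so it fixes all 20 arms at once.
- The reading most favourable to the plan puts the draw after consent in block 1, as section 6.2.1 might suggest. Block 1 must be treated within a week of enrolment, so the draw has been made by then.
- Blocks 2 to 5 remain: 4 × 4 = 16 sites, and 16 × 20 = about 320 of 400 residents. All are recruited after allocation. Anyone who knows which sites form each set can then infer their arms.

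**2. Reproducing the plan's own figure (section 9.1.1).**
- Inputs: 400 residents, 80% retention, so 160 per arm; cluster size 16; intra-site correlation 0.077; control rate 12%; two-sided alpha 0.05; 80% power.
- Design effect = 1 + (16 − 1) × 0.077 = 2.155. Effective n per arm = 160 / 2.155 = 74.2.
- Unpooled SE at 12% v 30.3% = √[(0.12×0.88 + 0.303×0.697)/74.2] = 0.0653. Minimum detectable difference = (1.96 + 0.84) × 0.0653 = 0.183, giving 12% + 18.3% = 30.3%. This matches the plan.
- A pooled test at the same effective n gives 78.5% power at 30.3%.

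**3. Selection favouring intervention, with no true effect.** The documents give no size for differential enrolment, so the share and the adoption rate below are assumptions. The middle rate, 31.3%, is the pilot's figure for residents who received the intervention (section 9.1.1).
- Shift = share × (adoption rate − 0.12).
- Null SE = √(2 × 0.12 × 0.88 / 74.2) = 0.0533.
- Rejection rate = Φ(shift/SE − 1.96) + Φ(−shift/SE − 1.96).

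| Extra motivated share | Their adoption rate | Shift (points) | Type I error |
|---|---|---|---|
| 10% | 25% | 1.3 | 5.7% |
| 20% | 25% | 2.6 | 7.8% |
| 10% | 31.3% | 1.9 | 6.5% |
| 20% | 31.3% | 3.9 | 11.2% |
| 10% | 40% | 2.8 | 8.2% |
| 20% | 40% | 5.6 | 18.3% |

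For the last row, a pooled test that re-estimates the SE gives about 16%.

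**4. Selection favouring control.** If enrolment differences lift the control rate by 5 points, to 17%, while the intervention rate stays at 30.3%, pooled-test power falls from 78.5% to 47.9%. A 2-point lift gives 67.0%.

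**The case against.** **A reader might infer** that all 20 sites are allocated before any resident is screened, and that staff recruit knowing the arm. The documents do not establish either. The first is the natural reading of sections 3.1 and 4.2, but neither section dates the draw, and sections 6.1 and 6.2.1 point the other way. The second rests on section 4.7 and on the shared label of study staff. The plan does not say that recruiters are told the arm, that the same individuals recruit and counsel, or that flyers mention timing. What stands is that at least 16 sites follow the draw and that no concealment is described.

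**The plan has safeguards.**
- Section 4.1.1 requires CO-verified smoking of at least 5 cigarettes a day and smoking in the home. This narrows who can enter. It does not select on willingness to change.
- Section 4.2 invites all residents at a site and collects site totals to estimate the proportion enrolled. That can reveal unequal uptake, but the analysis does not use it.
- Section 9.3 checks baseline characteristics against arm, and section 9.3.2 adds a propensity adjustment if key factors are imbalanced. This is conditional and reaches only measured factors. Motivation is not a named measure in section 7.1; the attitude and barrier items there are at best proxies.

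These reduce the risk but do not remove it.

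**Direction and size are uncertain.** Wait-list residents are also promised the intervention, so motivated residents have a reason to join in either arm. A 40% adoption rate without an effective intervention is generous beside 31.3% in the treated pilot. Both points are fair, which is why the working gives a range and both directions.

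**Conclusion.** The concern holds in limited form. Under the plan's single draw and monthly blocks, at least 16 of 20 sites (about 320 residents) are recruited after allocation, and nothing in the documents keeps the arm from recruiters or residents. Sections 3.1 and 4.2 cannot be squared with sections 6.1 and 6.2.1 on when randomisation happens.

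The amount of bias is unknown. Under the stated assumptions, type I error could rise from 5% to between about 6% and 18%, or power at 30.3% could fall from about 78% to 48% if selection runs the other way. The documents do not show that such selection will occur, and they do not dispute or alter the 30.3% figure, which reproduces.

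This should be fixed before recruitment: the change is cheap, and differential enrolment cannot be fully undone afterwards.

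**What to change.** 1. Keep the balanced restricted randomisation, with the statistician holding both set membership and allocation concealed. If set membership is known, releasing one block reveals the rest. The alternative is to draw 2:2 within each block under the same balance constraints, amending sections 3.1 and 9.1.3.
2. In each block of four, complete advertising, consent and baseline at all four sites with one arm-neutral script. Only then release that block's allocation.
3. Start the delivery window and the 3- and 6-month follow-up clocks at release, in both arms. The sponsor should set a delivery window that is feasible for two sites at once: 2 × 20 = about 40 one-hour sessions per block.
4. Align training of housing staff with release.
5. Analyse everyone consented before release by intention to treat.
6. Amend sections 4.2, 6.1 and 6.2.1 so that all state the same order of consent, baseline and site allocation.

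**Cost.** Early enrolees in a block may wait up to about a month between consent and study start. Some may drop out before release, and counselling will be scheduled more tightly. Section 4.2 already allows a one-to-two-month extension to recruitment. The sample size and primary model do not change.

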4.3 Inclusion of Women and Minorities

4.3.1 Eligibility of Women and Minorities

The proposed study aims to enroll 400 residents from 20 permanent supportive housing (PSH) sites who are representative of the racial/ethnic and gender diversity of the population in PSH in the San Francisco Bay Area (Aim 1). Because all residents in PSH have experienced homelessness, we believe that estimates of targeted enrollment for our study would be most accurate if it reflected the racial/ethnic and gender diversity of people who have experienced homelessness in the San Francisco, Alameda, San Mateo, and Santa Clara counties where PSH properties are located. We relied on point-in-time counts and assessments of homelessness and housing instability in each county to obtain these estimates. San Francisco county: In 2017, there were 7499 unsheltered or publicly sheltered homeless persons in San Francisco, of whom 35% were white, 34% were black, 3% were American Indian/Alaskan Native, 4% were Asian, 2% were Native Hawaiian/Pacific Islander, 22% were Hispanic/Latino, 22% were mixed race, and 33% were women.¹²⁵ Alameda county: In 2017, there were 5629 unsheltered or publicly sheltered homeless persons in Alameda, of whom 30% were white, 49% were black, 3% were American Indian or Alaskan Native, 2% were Asian, 1% were Native Hawaiian/Pacific Islander, 17% were Hispanic/Latino, 15% were mixed race, and 41% were women.¹²⁶ San Mateo county: In 2017, there were 1,253 unsheltered or publicly sheltered homeless persons in San Mateo county, of whom 72% were white, 16.3% were black, 3.3% were American Indian/Alaskan Native, 2.7% were Native Hawaiian/Pacific Islander, 1.8% were Asian, 3.9% were mixed race, 26.6% were Hispanic/Latino and 25.3% were female.¹²⁷ Santa Clara county: In 2017, there were 7,394 unsheltered or publicly sheltered homeless people in Santa Clara county, of whom 47% were white, 14% were black, 3% were American

Indian/Alaskan Native, 20% were Native Hawaiian or Pacific Islander, 3% were Asian, 44% Latino, 13% were mixed race, and 34% were female.¹²⁸

4.3.2 Recruitment of Women and Minorities

The study recruitment strategy aims to achieve representation of minority groups that reflects the demographics of the affected population in the catchment area.

4.4 Inclusion Across the Lifespan

4.4.1 Age Range of Participants

The proposed study will include all adult participants across the lifespan, without any restrictions based on age, gender or race/ethnicity. Eligible participants will include those who are ≥ 18 years of age. However, no children under the age of 18 years of age will be included in this study of adult cigarette smokers. While PSH residents who participate in the smoke-free home intervention study might have children living with them in their home, the unit of analysis will be the residents and not their children. However, we will gather information both quantitatively and qualitatively on whether children live in their homes, and the influence, if any, that children had on residents' adoption of a voluntary smoke-free home.

4.4.2 Study Design/Recruitment Considerations Related to Age Groups

The study design and recruitment strategy aim to achieve representation of age groups that reflect the demographics of the affected population.

4.5 Participant Registration

A written, signed, informed consent form (ICF) and a Health Insurance Portability and Accountability Act (HIPAA) authorization must be obtained before any study-specific assessments are initiated. A copy of the signed ICF will be given to the subject and a copy will be filed in the medical record. The original will be kept on file with the study records.

All participants consented to the study will be registered in OnCore®, the UCSF Helen Diller Family Comprehensive Cancer Center Clinical Trial Management System (CTMS). The system is password protected and meets HIPAA requirements.

4.6 Randomization/Assignment to Intervention

See Section 3.1

4.7 Blinding

Not applicable

5 Study Intervention

5.1 Administration and/or Delivery of Study Intervention

Smoke-free home PSH resident intervention. Study staff will deliver a one hour, one-on-one counseling to PSH residents that includes: (1) a step-by-step guide on how to voluntarily adopt a smoke-free home, (2) information on SHS and thirdhand smoke, alternative combustible tobacco and nicotine product use, cannabis-tobacco co-use, effects of SHS on kids and pets,⁴⁰⁻

⁴³(3) a worksheet on calculating personal costs related to tobacco use, and (4) pledges to designate one's home smoke-free.

Smoke-free home PSH staff intervention. Study staff will conduct a two-hour training for PSH staff on how to provide referrals to smoking cessation programs using materials previously developed from the UCSF's Rxforchange curriculum for service providers.⁷⁹ PSH staff play an integral role in residents' lives by facilitating access to services, whether they be mental health, substance use or healthcare services. In keeping with that model, our training is directed toward empowering PSH staff to provide referrals to local cessation services using the ask, advise, and refer approach,⁸⁰ which has been shown to increase engagement in cessation treatment. The training will address nicotine addiction, tobacco use among PSH residents, pilot data, brief cessation counseling (ask, advise, and refer), and local resources for cessation. Because PSH resident-PSH staff encounters will take place as part of routine care, we will request permission from a random sample of staff and resident dyads (n=40) to record these interactions to assess fidelity.

Usual care. The current standard of care includes no interventions for smoke-free home adoption or referrals to smoking cessation resources.

5.2 Interventionist Training and Tracking

Training the 'interventionist'. The PI will train study staff to deliver the one-on-one counseling intervention to PSH residents on how to voluntarily adopt a smoke-free home. The PI will also train study staff to deliver a training to PSH staff on how to provide referrals to smoking cessation programs. To assess fidelity of the intervention roll-out, the PI will observe and evaluate study staff during intervention delivery and provide verbal feedback.

